12.1.1 SEVERITY OF ADVERSE EVENTS

The severity of an adverse event is to be indicated by the investigator according to the following scale:

1 Mild Awareness of sign or symptom, but easily tolerated

2 Moderate Discomfort enough to cause interference with usual activity

3 Incapacitating with inability to work/perform usual activity or to Severe

significantly affect clinical status

12.1.2 RELATEDNESS OF ADVERSE EVENT

The relationship of an adverse event to investigational product is to be assessed by the investigator according to the following definitions:

Related:

There is a relationship between the event and treatment with the investigational product or there is a reasonable possibility that there is evidence to suggest a causal relationship, follows a temporal relationship of the event to study drug administration and cannot be reasonably explained by other factors (such as the subject's clinical state, concomitant therapy and/or other interventions). The following types of evidence would suggest a causal relationship between investigational product and AE: a single occurrence of an event that is uncommon and known to be strongly associated with drug exposure (angioedema, hepatic injury, Stevens-Johnson Syndrome), one or more occurrences of an event that is not commonly associated with drug exposure, but is otherwise uncommon in the population exposed to the drug (tendon rupture), an aggregate analysis of specific events observed in a clinical trial that indicated those events occur more frequently in the drug treatment group than in a concurrent or historical group.

Not Related: There is not a possibility that the AE is related to the investigational product. There is Data is available to clearly identify an alternative cause for the event (e.g., antigen in a case of suspected drug-induced hepatitis, hemorrhage due to mechanical injury)

Note: An alternative etiology must be provided by the investigator if the event is deemed Not Related

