10 CONCOMITANT MEDICATIONS

Medications in use at study entry should be documented on the CRF. Documentation should include medications that subjects take on an elective or as needed basis. If medications are related to a pre-existing (concomitant) condition or disease this condition or disease will be documented on the Medical History page of the CRF. In general, the addition of a concomitant medication upon or after treatment represents a new adverse event. Worsening of a condition present upon entry or noted as medical history also represents a new AE.

The following medications, preparations, and treatments are prohibited during the study as follows:

- 1. All topical skin care products on the face. Non-medicated facial cleansers are allowed. The use of Latisse is allowed. Makeup is allowed but must be removed for study visits.
- 2. All facial treatments including toxins, fillers, microdermabrasion, IPL, peels, facials, laser treatments, tightening treatments, and facial laser hair removal. Waxing and threading is allowed.
- 3. Oral or topical retinoids.
- 4. Alpha or beta hydroxy acids.

The use of other OTC and prescription medications, exclusive of the medications, preparations, and treatments listed above, are permitted after initiation of the study drug, but must be captured on the appropriate CRF page. If a patient uses any of the above prohibited treatments after initiation of the study drug, contact the medical monitor.

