12 SAFETY EVALUATIONS

12.1 SAFETY ASSESSMENTS – ADVERSE EVENTS (AE)

An AE is any untoward medical occurrence in a subject or clinical investigation subject administered a study product and which does not necessarily have a causal relationship with the study product. An AE can therefore be any unfavorable and unintended sign (including a clinically significant abnormal laboratory finding), symptom, or disease temporally associated with the use of an investigational or marketed study product, whether or not considered related to the investigational or marketed study product.

AEs include any illness, sign, symptom, or out-of-range AND clinically significant laboratory finding that has appeared or worsened during the course of the clinical study, regardless of causal relationship to the study product(s). The collection of non-serious AE information should begin at initiation of study product. Serious AEs (SAEs) should be collected from the time that the subject provides informed consent, which is obtained prior to the subject's participation in the clinical study, i.e., prior to undergoing any study-related procedure and/or receiving investigational product, through and including 30 calendar days after the last administration of the investigational product. Any SAE occurring after study completion must be promptly reported if a causal relationship to investigational product is suspected.

An evaluation of adverse experiences will be performed at each visit. The subject will be questioned to determine if any adverse events have been experienced since the last visit. All adverse events, regardless of perceived relationship to investigational product, will be reported and recorded on the appropriate case report forms. Any significant new abnormality will be recorded and followed until the abnormal finding returns to normal for that subject.

When a concomitant medication/therapy is reported during the study that is not related to medical history, a corresponding Adverse Event form will be completed and the reason for the treatment documented.

When a drug-related adverse event persists at the end of the study, the investigator will conduct follow-up contacts with the subject until the investigator/sponsor agree the event is satisfactorily resolved and/or stabilized.

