14.2.5 ANALYSIS OF SAFETY

14.2.5.1 Analysis of Adverse Events

Safety analysis will include assessment (number and %) of all treatment-emergent AEs, any serious AEs, treatment-related AEs, and AEs leading to study discontinuation for each treatment group.

All AEs will be coded by the Medical Dictionary for Regulatory Activities (MedDRA).

Treatment-emergent adverse events (TEAEs) are defined as those AEs that either have an onset time on or after the start of study drug until the end of study.

Treatment-emergent AEs will be summarized for each treatment group by the overall incidence of at least one event, incidence by system organ class, and incidence by system organ class and CONFIDENTIAL AND PROPRIETARY INFORMATION OF OMP, INC.

preferred term. Each subject will be counted only once for each of the rates, regardless of the number of occurrences (events) the subject experiences. Treatment-emergent AEs will be summarized by severity and by relationship to study product.

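### The Related and Not Related definitions in Protocol Section 12.1.2 leave some adverse events in neither category, with no default, so for those events the treatment-related AE rate depends on the rater

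*Protocol*

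**What the plan says.** **Related (Section 12.1.2).** The definition opens "There is a relationship between the event and treatment with the investigational product or there is a reasonable possibility". The possibility route is then qualified: the event must follow in time from use of the product and must be one that "cannot be reasonably explained by other factors". The factors named there are the subject's own condition, other therapy and other interventions.

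**Not Related (Section 12.1.2).** "There is not a possibility that the AE is related to the investigational product". The text goes on to refer to data that clearly identify another cause, and a note adds: "An alternative etiology must be provided by the investigator if the event is deemed Not Related".

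**Nothing in between.** There is no third level and no default. Section 12.1 asks for the investigator's opinion on how likely a causal link is, but points for this to a Section 14.1.2, which the protocol does not contain. Section 12.1.2 is therefore the only rule.

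**Where the label is used.** The synopsis names treatment-related AEs as a safety variable. Section 14.2.5.1 reports their count and percentage and adds: "Treatment-emergent AEs will be summarized by severity and by relationship to study product".

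**Competing causes that remain possible.** Section 10 states "Waxing and threading is allowed", and also permits make-up, Latisse and non-medicated cleansers. Section 8.1, criterion 3, selects for proneness to breakouts, and Section 10 counts worsening of a condition present at entry as a new AE.

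**The concern.** The two definitions use different thresholds. Related is barred by a reasonable alternative explanation. Not Related is barred by any possibility of a product role. An event with both features is barred from both.

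The study has a single arm, so the investigator's causality judgement is the only attribution the AE tables carry. That judgement is made and recorded at the site when the event is reported, so a later analysis plan cannot repair an incomplete rule. If two raters resolve the same kind of event differently, the treatment-related AE percentage reflects their habits as well as the product.

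**Working it through.** The protocol states no figure for related AEs, so there is nothing to reproduce. The check has two parts: whether the definitions are exhaustive, and how far the rate can move.

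**1. Exhaustiveness.** Describe each event by five yes/no facts taken from Section 12.1.2:

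- R: a relationship is established
- P: a relationship is possible
- T: there is supporting evidence and a temporal link
- E: the event is reasonably explained by other factors
- C: another cause is clearly identified

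Drop the incoherent patterns (R without P, C without E). That leaves 3 (R,P pairs) × 2 (T) × 3 (E,C pairs) = 18 patterns.

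Related = R or (P and T and not E): 6 + 1 = 7 patterns. This is the generous reading, since it lets an established relationship qualify by itself.

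The sentence joining the two parts of Not Related is garbled, possibly by text conversion, so three readings were tried:

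| Reading of Not Related | Patterns | In both classes | In neither class |
|---|---|---|---|
| No possibility, and other cause identified | 2 | 0 | 18 − 7 − 2 = 9 |
| No possibility only | 6 | 0 | 18 − 7 − 6 = 5 |
| Either condition is enough | 10 | 2 | 18 − 7 − 10 + 2 = 3 |

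The pattern at issue (not established, possible, temporal link, reasonably explained by something else, other cause not clearly identified) is in neither class under all three readings. The finding therefore does not rest on how the garbled sentence is resolved.

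**2. A concrete case.** A subject develops irritation after waxing while using the product. The product is a possible cause, so Not Related fails. Waxing is a reasonable explanation, so Related fails. A breakout in a breakout-prone subject works the same way, with the subject's own condition as the other explanation.

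**3. Effect on the rate.** Let c be subjects with a clearly related AE and g be subjects whose only candidate events fall in the gap. The denominator is taken as 40, the planned enrolment. The rate is c/40 if gap events are labelled Not Related and (c + g)/40 if labelled Related, a spread of g/40 or 2.5 percentage points per gap subject. The counts below are assumptions; the protocol gives none. Intervals are exact Clopper-Pearson 95%.

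| c | g | Gap labelled Not Related | Gap labelled Related |
|---|---|---|---|
| 4 | 2 | 4/40 = 10% (2.8–23.7%) | 6/40 = 15% (5.7–29.8%) |
| 4 | 4 | 4/40 = 10% (2.8–23.7%) | 8/40 = 20% (9.1–35.6%) |
| 4 | 8 | 4/40 = 10% (2.8–23.7%) | 12/40 = 30% (16.6–46.5%) |
| 8 | 4 | 8/40 = 20% (9.1–35.6%) | 12/40 = 30% (16.6–46.5%) |
| 8 | 8 | 8/40 = 20% (9.1–35.6%) | 16/40 = 40% (24.9–56.7%) |

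**The case against.** **A working default already exists.** Not Related carries a burden of proof, so an event that cannot meet it is left with Related. This has some force where no other cause can be named. It does not settle the confounded event: the investigator can name waxing or the subject's breakout tendency and so satisfy the note, while the wording of Related turns the event away. Either box can be defended.

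**The rate is not undefined.** A reader might infer that it is. It is not: there are two boxes, the investigator ticks one, and a percentage results. The defect is dependence on the rater. Nor does the text show that two sites would disagree. There may be only one site, and at most one can say that raters may differ.

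**The gap is narrow.** A reader might infer that it covers the typical facial reactions. The protocol does not rank reactions. Dryness/scaling, erythema, burning/stinging and itching are graded at each visit and summarised without a causality judgement (Sections 12.2 and 14.2.5.2). Section 10 prohibits most other facial products and procedures, and Section 8.2 excludes active facial inflammation. Many local reactions may therefore have no other reasonable explanation and meet Related. This objection stands.

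**Clinical actions do not hang on the label.** The rule that begins "When a drug-related adverse event persists at the end of the study" suggests otherwise, as does the withdrawal ground in Section 8.5.1. But Section 12.1 also has AEs followed to resolution or stabilization whatever their cause. Section 8.5.1 allows withdrawal for safety or other reasons. Section 12.1.3 has SAEs reported whether related or not, and after completion the trigger is suspicion of a causal link, a different test from Related. This objection stands.

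**The aggregate-comparison example does no harm.** Section 12.1.2 lists it as one type of evidence, not as a condition, so it misclassifies nothing.

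**Conclusion.** The concern holds in a limited form. The two definitions are not exhaustive under any reading tried, and no other section supplies a default. For AEs with a possible product role and a plausible but unproven other cause, the treatment-related AE rate and the summary by relationship depend on the rater. This is a flaw in a rule the protocol states, and it feeds a named safety result.

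The size cannot be derived from the protocol. With 40 treated subjects it is 2.5 percentage points per subject whose only candidate events fall in the gap, and the counts tabulated are illustrations. The conclusion assumes that the five facts capture the definitions and that Section 12.1.2 is the rule given to sites. Total treatment-emergent AEs, SAEs, AEs leading to discontinuation and the tolerability grades do not change.

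**What to change.** Rewrite Section 12.1.2 so that the categories are complementary and carry a default:

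- **Related:** there is a reasonable possibility that the product caused or contributed to the event, even if another factor may also have contributed.
- **Not Related:** there is no reasonable possibility, and the alternative etiology is recorded.
- **Default:** an event without a clearly identified alternative cause is classed Related.

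On the 18 patterns above, reading P as a reasonable possibility, this puts 12 in Related by definition, 4 in Related by default and 2 in Not Related, with none left over and none in both.

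Carry the same wording into the AE form instructions, and correct the Section 12.1 cross-reference so that it leads to this definition. Moving the aggregate-comparison example to the sponsor's review is optional tidying.

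The opposite default, or a third level with a stated rule for which levels count in the rate, would also close the gap. The version above leans toward attributing events to the product.

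The cost is one paragraph and the form wording, with no new data. The downside is that the reported treatment-related AE rate may be slightly higher.

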12.1.3 SERIOUS ADVERSE EVENTS (SAE)

If either the sponsor or the investigator believes that the event met seriousness criteria, the event must be considered serious and evaluated by the sponsor for expedited reporting (21 CFR 312.32(a)).

As with the definition of serious, the determination of whether an AE is life-threatening can be based on the opinion of either the investigator or sponsor (21 CFR 312.32(a)).

A SAE is defined (21 CFR 312.32) as any untoward medical occurrence occurring at any dose that results in any of the following outcomes:

- results in death,
- is life threatening (defined as an event in which the Subject was at risk of death at the time of the event; it does not refer to an event which hypothetically might have caused death if it were more severe),
- requires inpatient hospitalization or prolongation of existing hospitalization,
- results in persistent or significant disability/incapacity,
- results in a congenital anomaly or birth defect, or
- Is an important medical event (defined as a medical event(s) that may not be immediately life-threatening or result in death or hospitalization but, based upon appropriate medical and scientific judgment may jeopardize the patient/Subject or may require medical or surgical intervention to prevent one of the other serious outcomes listed in the definition above). Examples of such events include, but are not limited to, allergic bronchospasm requiring intensive treatment in an emergency room or at home; blood dyscrasia or convulsions that do not result in inpatient hospitalization; the development of drug dependency or drug abuse.
- Hospitalization solely for the purpose of diagnostic tests, even if related to an AE, elective hospitalization for an intervention which was already planned before the inclusion of the subject in the study, and admission to a day-care facility may not themselves constitute sufficient grounds to be considered a SAE. Hospitalization is defined as being admitted to a hospital as an in-patient for greater than 24 hours.

Any SAE that occurs during the study whether related to the treatment or not, expected or not, will be reported immediately (within 24 hours of knowledge of occurrence) by telephone and confirmed facsimile transmission/email to the Medical Monitor and/or Project Manager listed in this protocol. If only limited information is initially available, follow-up reports are required.

Information regarding serious adverse events will be transmitted to the sponsor using the Serious Adverse Event From, which must be signed by a member of the investigational staff. The initial report of a serious adverse event may be made by facsimile (fax) or telephone. It is

preferable that serious adverse events be reported via fax. Subsequent to a telephone report of a serious adverse event, A Serious Adverse Event Form must be completed by the investigational staff and transmitted to the sponsor within 1 business day. Serious adverse events require notification within 1 business day to the Sponsor or its designated representative beginning from the time that the subject provides informed consent, which is obtained prior to the subject's participation in the clinical study, i.e., prior to undergoing any study-related procedure and/or receiving investigational product, through and including 30 calendar days after the last administration of the investigational product. Any SAE occurring after study completion must be promptly reports if a causal relationship to investigational product is suspected.

The immediate SAE report should be followed-up within one business day by electronic mailing (e-mail) the completed SAE form to: [contact]. Please also copy the following email addresses on the distribution of the SAE form: [contact]; [contact]; [contact].

12.1.4 PREGNANCY

All female subjects of childbearing potential must use an effective method of birth control during the course of the study, in a manner such that risk of contraceptive failure is minimized. Abstinence is allowed as a birth control method.

Before enrolling a female subject of childbearing potential in this clinical trial, the Investigator must review the following information about study participation:

- Informed consent/assent requirements
- Contraceptives in current use

Following review of this information and appropriate subject counseling, the Investigator or designee and the subject must sign the Informed Consent before study enrollment.

During the study, all female subjects of childbearing potential should be instructed to contact the Investigator immediately if they suspect they might be pregnant (e.g., missed or late menstrual period).

If a subject or Investigator suspects that the subject may be pregnant prior to study enrollment, the investigational product must be withheld until the results of laboratory pregnancy testing are available. If pregnancy is confirmed, the subject must not receive investigational product and must not be enrolled in the study. If pregnancy is suspected while the subject is receiving investigational product, the investigational product must immediately be withheld until the result of a urine pregnancy test is known. If pregnancy is confirmed, the study drug will be permanently discontinued and the subject will be followed until the pregnancy comes to term. A Pregnancy Report form will be submitted, initially and quarterly through the end of the pregnancy, which includes the outcome of the pregnancy and any complications occurring

during the pregnancy or the delivery. The timelines and sponsor contact(s) for submission of pregnancy related information will follow those of SAEs above.

An event that is serious must be recorded on the Adverse Events CRF and requires expeditious handling to comply with regulatory requirements. All initial SAEs and follow up reports that contain change in causality must be forwarded to Obagi within 1 business day upon receipt of SAE. In addition, the serious adverse event form and other SAE-related forms must be completed accordingly.

Any serious or immediately life-threatening adverse event, including death, occurring while the subject is participating in a clinical study, irrespective of the investigator's opinion of causality (considered related or unrelated), will be reported immediately (within 24 hours of knowledge of occurrence) by telephone and confirmed facsimile transmission/email to the medical monitor listed in this protocol. If only limited information is initially available, follow-up reports are required. In the event of death, if an autopsy is performed, a copy of the report should be sent to medical monitor / sponsor.

The investigator is also responsible for notifying the IRB within the time frame established by the IRB.

12.2 TOLERABILITY EVALUATIONS

The investigator will assess the tolerability of the Obagi 360 system at each visit. Tolerability will be graded on a 4-point scale (0 - none to 3 - severe) for each of the following:

- Dryness/Scaling
- Erythema
- Burning/Stinging
- Itching

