
Test product, dose and mode of administration:

Obagi 360 System consisting of: Obagi 0.5% retinol, Hydrafactor SPF30, and Exfoliating cleanser. The system will be used once daily for 3 months.

Reference therapy, dose and mode of administration:

None

Duration of treatment, enrollment and follow-up:

Duration of treatment period: 12 weeks

Criteria for evaluation:

- 1. Improvement in manifestations of photodamage assessed by the investigator using the Investigator's Skin Grading Assessment.
- 2. Assessment of improvement by the subject using the Subject's Self-Assessment.

Safety:

Safety variables include treatment-emergent adverse events (AEs), serious AEs (SAEs), treatment related AEs, and AEs leading to study discontinuation.

The investigator will assess the tolerability of the product at each visit.

Sample size:

Forty subjects will be enrolled. Forty (40) subjects are adequate to obtain information on the anti-aging effects of the Obagi 360 system.

Statistical methods:

The effect of the Obagi 360 system on photodamage will be evaluated using the Investigator's Skin Grading System. The changes from baseline in the scores will be summarized and tested for significance using the paired T-test for each time point. In addition, a summary of the distribution or scores (improvement or worsening) will be summarized and categorized as the number and proportion of subjects "Improved", "Equal to" or "Worse" than baseline.

For the Subject's Self-Assessment, the response to each question will be summarized by the proportion of subjects in each category. No statistical testing will be performed on the Subject's Self-Assessment.

Safety will be summarized by the incidence of adverse events over the study by body system and preferred term. The tolerability will be summarized by the proportion of subjects with none, mild, moderate, and severe for each assessment by visit.

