7.3 SCHEDULE OF STUDY PROCEDURES

A table outlining the schedule of procedures for this study is presented in Table 1.

Table 1 Procedures Flow Chart

PROCEDURES	BASELINE (DAY 0)	DAY 14 (± 2 Days) and DAY, 28, 56, and 84 (± 5 Days)
	Visit 1	Visits 2 through 5
Obtain Informed Consent, HIPAA Authorization	X	
Obtain Photographic Release Form	X	
Review Inclusion/Exclusion Criteria	X	
Review Medical History	X	
Obtain Subject Demographics	X	
Conduct Investigator's Skin Grading Assessment	X	X
Urine Pregnancy Test ¹	X	X
Obtain Photographs	X	X
Conduct Subject's Self-Assessment ²		X
Assign Subject Number	X	
Review Obagi 360 Application ³	X	X
Dispense/Collect Obagi 360 System	X	X
Assess Tolerability		X
Review Concomitant Medications	X	X
Review Adverse Events		X
Review Compliance with Study Procedures		X

UPT obtained on subjects of child bearing potential only.

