7.4 DURATION OF SUBJECT PARTICIPATION

The duration of the treatment is daily for 12 weeks. Subjects will be expected to come to the study center for the baseline visit and 4 additional study visits.

Subject's Self-Assessment of improvement Questionnaire (Appendix 2) will only be administered at Visit 2 and Visit 3

Subjects receive instruction during visit on how to apply study treatment product. The first application of study treatment product to the face will be applied at the conclusion of the Baseline visit as part of the Study Treatment Dispensing and Application Training.

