13.1 VISIT 1/BASELINE VISIT (STUDY DAY 0)

The following pre-study screening procedures should be completed prior to initiating study treatment:

- 1. Obtain a signed and dated subject informed consent form and authorization to use and disclose medical information prior to performing any study-specific procedures;
- 2. Obtain a signed and dated Photographic Release Form prior to obtaining any photographs
- 3. Collect demographic information including date of birth, sex, race, ethnicity and Fitzpatrick skin type;
- 4. Collect a medical history (only relevant, current/ongoing diseases/conditions and past surgeries/procedures as determined by the investigator);
- 5. Review inclusion and exclusion criteria;
- 6. Upon qualifying for the study, subjects will be assigned a study number (See Section 8.4);
- 7. Conduct Investigator's Skin Grading Assessment, see Section 11.1;
- 8. Obtain photographs. For details instruction on obtaining photographs, see Section 11.2;
- 9. A urine pregnancy test will be performed on females of child-bearing potential.
- 10. Review and record concomitant medications;
- 11. Dispense study product. Complete the product accountability CRF form;
- 12. Instruct subject in the application of the Obagi 360 system and provide written instructions;
- 13. Schedule the next visit with the subject on study Day 14 (\pm 2 days).

13.2 VISITS 2 THROUGH 5 (STUDY DAY 14 [\pm 2 DAYS], AND STUDY DAYS 28, 56, AND 84 [\pm 5 DAYS])

The following procedures will be performed at these visits:

- 1. Conduct Investigator's Skin Grading Assessment, see Section 11.1;
- 2. Obtain photographs. For details instruction on obtaining photographs, see Section 11.2;
- 3. A urine pregnancy test will be performed on females of child-bearing potential at the End of Study Visit.
- 4. Conduct subjects' self-assessment see Section 11.3, Appendix 2 and Appendix 3;
- 5. Assess tolerability of the Obagi 360 system;
- 6. Review and record concomitant medications;
- 7. Review and record adverse events:
- 8. Dispense/collect study product. Complete the product accountability CRF form;
- 9. Review with subject the application of the Obagi 360 system;
- 10. Schedule the next visit with the subject or end subject participation at Visit 5.

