14.2.5.2 Analysis of Tolerability

Tolerability will be assessed using the scale in Section 12.2. For each of the assessments, the proportion of subjects experiencing none, mild, moderate, and severe will be summarized by visit.

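### No tolerability grade is scheduled before the first application, so the by-visit tolerability table cannot separate irritation present at entry from irritation that arises on treatment

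*Protocol*

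**What the plan says.** On timing, the narrative sections and the schedule differ.

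- Section 12.2: "The investigator will assess the tolerability of the Obagi 360 system at each visit". The synopsis, under Safety: "The investigator will assess the tolerability of the product at each visit". Neither makes an exception for Baseline.
- Section 7.3, Table 1: the row "Assess Tolerability" is blank under Baseline and marked under Visits 2 through 5.
- Section 13.1 lists 13 Baseline steps, none of which is tolerability. In Section 13.2 (Visits 2 through 5), item 5 is "Assess tolerability of the Obagi 360 system".
- Section 7.4: "Subjects will be expected to come to the study center for the baseline visit and 4 additional study visits". On the start of treatment, Section 7.4 adds: "The first application of study treatment product to the face will be applied at the conclusion of the Baseline visit".

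On measurement, Section 12.2 says: "Tolerability will be graded on a 4-point scale (0 - none to 3 - severe) for each of the following". The four items are dryness/scaling, erythema, burning/stinging and itching. On analysis, Section 14.2.5.2 says that, for each assessment, "the proportion of subjects experiencing none, mild, moderate, and severe will be summarized by visit". The synopsis lists no reference therapy.

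**The concern.** A tolerability grade is a statement of severity on the day. It becomes evidence about the product only when set against something: a control group, or the same subject before treatment. This trial has no control group, and its detailed schedule collects no pre-treatment grade. A subject who enters with mild dryness and leaves with the same mild dryness appears in the Day 84 table exactly as does a subject who developed it on the product.

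Tolerability is one of the stated safety outputs. The efficacy scores are compared with baseline (Section 14.2.3) and the tolerability grades are not. A statistical analysis plan, if there is one, could add a shift table, but it could not supply grades that were never taken.

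**Working it through.** The protocol gives no tolerability figure to reproduce, so the check is a comparison of the passages followed by an illustration.

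**Step 1: what will be collected.** There are five visits: Baseline plus four. Section 13 presents its lists as the full account of procedures, and they agree with Table 1. Sites that follow them will grade tolerability at four of the five visits and never before the first application.

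**Step 2: whether another Baseline item fills the gap.**

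- The investigator's skin grading (Sections 11.1 and 11.1.1) covers fine wrinkling, mottled hyperpigmentation, sallowness, loss of texture, pore visibility and breakouts. None of these is one of the four tolerability signs.
- Medical history (Section 13.1, item 4) records relevant conditions and procedures, not graded signs.
- Photographs (Section 11.2) are taken at Baseline. They may show redness or scaling but not burning, stinging or itching, and no grading of them for tolerability is planned.

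**Step 3: whether eligibility removes the problem.** Section 8.2 excludes current oral retinoids (2), products judged irritating (4), recent topical retinoids (5), recent hydroxy acids (6), a significant facial history of three skin diseases (7) and active facial inflammation (8). These lower the frequency of signs at entry. None clearly excludes mild dryness, slight scaling, occasional itch or faint redness.

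**Step 4: how far the table could be off.** For one sign at one visit, let b be the share of subjects with the sign at entry, assumed to persist, and t the onset rate among those without it at entry. Neither value is in the protocol; both are assumptions.

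- Reported proportion = b + (1 − b)t
- New onset among all subjects = (1 − b)t
- Difference = b, whatever the value of t

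| b | Expected subjects of 40 with the sign at entry | Reported / new onset, t = 10% | Reported / new onset, t = 20% |
|---|---|---|---|
| 0% | 0 | 10.0% / 10.0% | 20.0% / 20.0% |
| 5% | 2 | 14.5% / 9.5% | 24.0% / 19.0% |
| 10% | 4 | 19.0% / 9.0% | 28.0% / 18.0% |
| 20% | 8 | 28.0% / 8.0% | 36.0% / 16.0% |
| 30% | 12 | 37.0% / 7.0% | 44.0% / 14.0% |

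Worked line: with b = 0.10 and t = 0.20, 0.10 + 0.90 × 0.20 = 0.28 is reported, against 0.90 × 0.20 = 0.18 new onset. The 20% applies only to subjects free of the sign at entry, so 0.18 × 40 = 7.2 new cases are expected.

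The chance that at least one of 40 subjects enters with the sign is 1 − (1 − b)^40, which is 0.871 at b = 5% and 0.985 at b = 10%. Section 14.2.5.2 summarizes each sign separately, so b must be read per sign and not as the prevalence of any irritation.

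**The case against.** A reader might infer that irritation present before treatment will be counted as caused by the product. The protocol does not say so. The 0 to 3 grade carries no causality item, and the planned table is a plain description of severity. Relatedness is judged only for adverse events (Section 12.1.2). Adverse events must have appeared or worsened during the study (Section 12.1), and treatment-emergent events are defined by onset at or after the start of treatment (Section 14.2.5.1). An unchanged pre-existing sign should therefore not enter the adverse event tables. This objection stands against the causal reading. It leaves the descriptive table without a reference, and judging whether a sign is new or worse at Day 14 also depends on knowing how it was at entry.

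A reader might also call the timing a flat contradiction. That is too strong. Tolerability of a product not yet applied cannot literally be assessed. The protocol is equally loose about adverse event review, which Section 12.1 places at every visit and Table 1 only at Visits 2 to 5. On the other side, Section 11.3 says expressly that the self-assessment starts after Baseline. On either reading no pre-application grade is scheduled, and the point rests on that.

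Three further objections limit its weight. The exclusions and the Baseline photographs give partial protection. Tolerability is descriptive, is not tested and drives no decision rule. The likely error is to overstate irritation rather than to hide harm. The layout of a shift table can also be left to an analysis plan, but the collection of Baseline grades cannot.

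**Conclusion.** The point holds in a limited form. Under Table 1 and Section 13.1, no grade of the four signs exists before the first application, although Section 12.2 and the synopsis promise tolerability at each visit. With one arm and raw by-visit proportions, signs present at entry cannot be separated from treatment-emergent ones. The table may overstate irritation and cannot show who worsened or improved.

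The size is unknown. If a sign persists in all subjects who had it at entry, the excess over new onset among all subjects equals the entry prevalence b of that sign. It is zero if nobody enters with the sign and smaller than b if some signs resolve. Some subjects with a sign at entry may also worsen on treatment, which the raw table would not show. The 10% and 20% in the example are assumptions, not estimates from the protocol. The gap should be closed because only data collected at Baseline can do so, and the remedy is cheap.

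**What to change.** - In Table 1, mark tolerability in the Baseline column. In Section 13.1, add the four grades as a step before the first application. Both then agree with Section 12.2 and the synopsis.
- In Section 12.2, state that the Baseline grade records the signs before any product is applied.
- In Section 14.2.5.2, keep the raw proportions by visit. Beside them, report for each sign and visit the proportion of subjects whose grade worsened from baseline, with a shift table of baseline grade against visit grade.

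The cost is four 0 to 3 grades at a visit that already takes place, one CRF page and one table. Section 7.4 puts the first application at the end of the Baseline visit, so the grades fit without an added visit. Sample size and treatment do not change.
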